### **6.9.1 Progression free survival**

Progression free survival will be the primary endpoint of the study. Progression free survival will be measured from the time of initiation of SRS until the time of progression or death. Lesions that progress on initial TKI therapy will be treated with SRS or other locally ablative maneuver. Because of concern for potential antagonism between erlotinib and radiation as well as safety concerns, erlotinib will be held during SRS. This could potentially allow growth of non-treated, erlotinib-sensitive clones during this period, with later disease control on erlotinib. For this reason, non-treated lesions that progress between the pre-treatment and pre-erlotinib reinitiation evaluations will not be counted as progressive disease unless they also progress on the 1st follow-up imaging while on erlotinib. Further, areas treated with SRS are known to sometimes inflame as a consequence of therapy, with no actual disease progression. In clinical practice, radiologist and radiation oncologist assessment of these lesions are predictive of

long-term control. Therefore, clinician judgment will be used for both protocol and treatment decisions in evaluating whether a lesion treated with SRS that appears larger is actually progressive. In all cases, the same judgment must be used for both evaluation of control on study, and clinical decision making.

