#### 4.3 Erlotinib Treatment Dosage and Administration

Erlotinib (Tarceva®) will be administered per standard of care. Of note, patients with EGFR mutation often require substantially less than the standard dose to achieve efficacy. Thus, while the study recommends a standard starting dose, patients with known intolerance at this dose, but known tolerance with efficacy at a lower dose will be allowed to initiate at that dose. Erlotinib will be taken once per day on an empty stomach (one hour before, or two hours after food).

At the time of enrollment into the study, patients may already be on erlotinib therapy. For these patients, it is recommended (but not required) that erlotinib be discontinued 3 days prior to the initiation of SRS (i.e., if last dose of erlotinib is on a Sunday, SRS can be administered on Thursday). The study recommends that erlotinib be restarted 3 days after the completion of SRS. At the investigator's discretion, erlotinib may be started sooner (or never discontinued) but not later. .

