**Key to Time and Events Table**

 Unless otherwise noted, perform within 2 weeks prior to initiation of SRS or local ablative therapy. CT or PET within 4 weeks prior to the start of therapy

 Post SRS or local ablative therapy, pre-erlotinib unless patient enrolled in trial on erlotinib and continuing it through SRS, see section 4.3 (NOTE: this visit can occur on the last day of radiation)

 The initial 3 visits post erlotinib initiation will be performed at the enrolling site, and can take place every 8 weeks +/- 1 week; however, the tumor measurements at these visits should take place within 1 week (7 days) prior to the study visit. If patient progresses prior to the end of 6 months, then they will enter long-term follow-up (see section 6.5).

 For patients living a distance prohibitive for further travel to the enrolling site, visits after the initial 6 months on erlotinib (or after progression) for clinical care may be performed remotely by the patient's primary oncologist. In this case, records will be requested, specifically including doctors' notes, imaging reports, and CDs of imaging.

 This visit will be scheduled when a subject is withdrawn from study therapy prior to progression

 At the time of progression, choice of regimen for next treatment will be requested. If patient is not being treated at an enrolling site, these records may be obtained remotely. Imaging reports and images will be requested to ascertain the nature of and duration of response to the next line of therapy, when possible.

 Complete medical history at baseline, thereafter, symptom directed history

 Serum or urine pregnancy test for women of child bearing potential

 Serum chemistries include sodium, potassium, chloride, bicarbonate, magnesium, BUN, serum creatinine, glucose, calcium, total protein and albumin; liver function tests include total bilirubin, alkaline phosphatase, AST, and ALT)

 CT or PET scan-use consistent imaging throughout study; NOTE: the X at progression is there to indicate that progression was diagnosed via a tumor evaluation

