## 6.3 Treatment Assessments

### 6.3.1 Post SRS or other Local Ablation

- Symptom directed medical history and physical examination
- ECOG Performance Status (see appendix A)
- Laboratory evaluations: CBC with differential; serum chemistries (sodium, potassium, chloride, bicarbonate, magnesium, BUN, serum creatinine, glucose, calcium, liver function tests (LFTs; total bilirubin, alkaline phosphatase, AST, ALT), total protein, and albumin)
- Toxicity evaluation (for notation of any baseline toxicity) via NCI CTCAE v4.
- Blood sample for Veristat® assay: Draw 3.5 mL SST (gold -top) Vacutainer tube. See section 6.7 for additional details.

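### The section 6.9.1 exemption for growth around radiosurgery rests on an erlotinib hold that section 4.3 makes optional and on an evaluation for which no imaging is scheduled, so it cannot be applied as written

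*Combined protocol and SAP*

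**What the plan says.** **Premise and rule (section 6.9.1).** The section states without exception: "Because of concern for potential antagonism between erlotinib and radiation as well as safety concerns, erlotinib will be held during SRS". It reasons that untreated, still sensitive disease might grow during the hold and be controlled again later. For that reason alone, "non-treated lesions that progress between the pre-treatment and pre-erlotinib reinitiation evaluations will not be counted as progressive disease". The exemption lapses if the same lesions also progress on the first "follow-up imaging while on erlotinib".

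**Erlotinib around radiosurgery (section 4.3).** For patients already on the drug, "it is recommended (but not required) that erlotinib be discontinued 3 days prior to the initiation of SRS". On restarting, at the investigator's discretion, "erlotinib may be started sooner (or never discontinued) but not later".

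**Schedule.** The key to the Time and Events table provides for patients who do not stop: the post-SRS visit is "pre-erlotinib unless patient enrolled in trial on erlotinib and continuing it through SRS". Section 6.7 makes the same allowance for the blood sample. Section 6.3.1, "Post SRS or other Local Ablation", lists history and examination, performance status, laboratory tests, toxicity and a VeriStrat sample, but no CT or PET. The post-SRS cell of the tumor evaluation row in section 6.1 is empty.

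**Use of the endpoint (sections 8.2 and 8.3).** Median PFS is estimated by Kaplan-Meier. The proportion progression free at 3 months is tested against 50% with a one-sided exact binomial test in 40 patients.

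**The concern.** The exemption is part of the definition of the primary endpoint, and it needs two things: a patient who is off erlotinib over radiosurgery, and a tumor evaluation before the drug is restarted. The operative text guarantees neither. The amendment summary records that participating sites differ on the hold, so patients who continue are to be expected.

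For a patient who continues, there is no restart from which to define the second evaluation, and the stated reason for excusing growth (time off drug) does not apply. For a patient who stops, no scheduled imaging marks the end of the exempt interval. Someone will then have to decide case by case whether growth counts, in an open single-arm trial whose 3-month result turns on a few patients.

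**Working it through.** **1. Can the rule be run on the planned schedule?**

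| Rule needs (6.9.1) | Elsewhere in the plan |
|---|---|
| Erlotinib held over SRS | Recommended only; may never be stopped (4.3) |
| Pre-treatment evaluation | CT or PET within 4 weeks before therapy (6.2) |
| Evaluation before erlotinib restarts | No tumor evaluation in the post-SRS column (6.1) or in 6.3.1 |
| First follow-up imaging on erlotinib | Visit 8 weeks ± 1 week after erlotinib initiation, scan within 7 days before it (6.1) |

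Section 6.9.1 says evaluations, not scans. The only scheduled evaluation at that point is clinical, and a symptom-directed history and examination cannot establish RECIST 1.1 progression of imaged lesions. On the planned schedule the exemption is never triggered. It comes into play only if an unscheduled scan is done.

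**2. What happens if an unscheduled scan exists?**

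- Patient who stopped: the rule applies, but the requirement that the lesion also progress at first follow-up names no reference scan. Let S be the pre-treatment sum, with change confined to non-treated lesions and the 5 mm minimum met. Suppose the sum is 1.2 × S at the interim scan and unchanged at first follow-up. Against the pre-treatment scan, (1.2S − S)/S = 20%, which is progression under 6.9.10. Against the interim scan, (1.2S − 1.2S)/1.2S = 0%, which is not. Section 6.9.10 takes the smallest sum since treatment started, including baseline, which favors the first reading, but 6.9.1 does not say so.
- Patient who continued: there is no restart, so the rule is undefined. If it were applied, it would waive growth on drug only where that lesion does not also progress at first follow-up.
- Either way, if exempted growth is confirmed, 6.9.1 does not say whether progression is dated at the interim or the follow-up scan.

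**3. Timing against the 3-month landmark (13.0 weeks).** The documents give no single SRS duration; I assume d = 1 to 15 days, with a gap g = 0 to 3 days to restart.

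- First scan, earliest (d = 1, g = 0): (0 + 0 + 7×7 − 7)/7 = 6.0 weeks after SRS start.
- First scan, latest (d = 15, g = 3): (14 + 3 + 9×7)/7 = 11.4 weeks.
- Second scan, earliest, with both visit windows run short: (0 + 0 + 14×7 − 7)/7 = 13.0 weeks.

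The first scan therefore largely decides the 3-month status.

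**4. The plan's own figures.** With n = 40 and null 50%, P(X ≥ 25) = 0.0769 and P(X ≥ 26) = 0.0403, so success needs 26 of 40. Power at 70% is P(X ≥ 26 | 40, 0.70) = 0.807, matching the stated 80%. The exact 95% interval for 26/40 is 48.3% to 79.4%, matching the table in 8.2.

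**5. Sensitivity to misclassification (assumed; the documents give no rate).** Each patient is 1/40 = 2.5 points. Shift the probability of being counted progression free by k/40 and keep the cut-off at 26.

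| k of 40 | Power, p = 0.70 − k/40 (wrongly progressed) | Type I error, p = 0.50 + k/40 (wrongly progression free) |
|---|---|---|
| 0 | 80.7% | 4.0% |
| 1 | 69.9% | 7.6% |
| 2 | 57.2% | 13.3% |
| 4 | 31.7% | 31.7% |

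The last row agrees because both shifts arrive at p = 0.60.

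**The case against.** A reader might infer more: that the rule does misclassify progression, too strictly in patients who hold erlotinib and too leniently in those who continue, so that the 3-month rate partly reflects site practice. The documents do not support that.

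- **Patients who hold.** The rule expressly counts lesions that also progress at first follow-up. With the pre-treatment scan as reference, progression at that scan counts whether or not an interim scan was done. On this reading the rule only prevents an early call, and with no interim scan no early call can be made. A wrongly counted progression arises only if the interim scan was meant as the reference, which the text neither says nor excludes.
- **Patients who continue.** A wrongful waiver needs three things together: an unscheduled scan, progression on it, and no progression of that lesion at first follow-up. The wording does not clearly reach a patient who never restarts.
- **Both at once.** If no interim scan is done, nobody is exempted, so the two errors cannot both follow from the planned schedule.
- **Progression date.** Under the timing assumed above, either date falls before 3 months. The missing date can move the Kaplan-Meier curve but not the 3-month result, and only after an unscheduled scan.

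All of this stands, and it rules out any claim about the size or direction of bias. It can also fairly be said that 6.9.1 looks like wording left behind when the hold became optional. That explains the conflict without removing it: the rule still has a contradicted premise, no scheduled data, an unstated reference scan and no progression date.

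**Conclusion.** The point holds as a defect of definition. Section 6.9.1 contradicts section 4.3 in current text. The exemption cannot be applied on the schedule in 6.1 and 6.3.1, and it is undefined for patients who continue erlotinib. Where an unscheduled scan exists, it could waive growth on drug in such a patient, limited by the follow-up clause.

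The number of patients affected and the direction of any error are unknown. The power and type I error figures show only how sensitive a 26-of-40 rule is to a few patients. They rest on assumed shares of 1 to 4 in 40 and are not estimates of bias. The correction is worth making because this is the primary endpoint, the first on-drug scan largely settles the 3-month status, and an unclear rule invites case-by-case readings in an open trial.

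**What to change.** Reconcile 6.9.1 with 4.3 and with 6.1/6.3.1. This review takes no view on whether erlotinib should be held. For the endpoint, section 6.9.1 should:

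- limit the exemption to patients who actually stopped erlotinib over SRS and had a scan before restarting, and apply ordinary RECIST 1.1 to non-treated lesions in all other patients;
- name the reference scan for deciding that a lesion also progresses at first follow-up;
- date confirmed progression at the first scan that showed it.

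Record in the eCRF whether erlotinib was held or continued, and report PFS and the 3-month rate with and without the exemption.

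The cost is amendment wording, one eCRF item and one sensitivity analysis. No scan is added.

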### **6.4 Evaluation at Progression**

At the time of progression on erlotinib, the time of documented progression will be recorded. If feasible, obtain blood sample for Veristat® assay: Draw 3.5 mL SST (gold -top) Vacutainer tube. See section 6.7 for additional details. At the time of progression, choice of regimen for next treatment will be requested. If patient is not being treated at an enrolling site, these records may be obtained remotely. Imaging reports and images will be requested to ascertain the nature of and duration of response to the next line of therapy, when possible.

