#### **6.9.2 Local control rate of SRS treated lesions**

As noted above, areas treated with SRS are well known to inflame after therapy. In these cases, the clinical judgment of the radiologist and radiation oncologist will be used to assess the local control of specific lesions. Of note, observation over time may be necessary for definitive assessment of some lesions.

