#### **8.2 Sample Size and Accrual**

No data exist at this time to define median progression-free survival on chemotherapy, following first-line erlotinib. However, the FDA has approved docetaxel, pemetrexed and erlotinib for second line therapy based on a median

PFS of 1.8-2.9 months, establishing a standard for minimally effective second line therapy.

Study	Regimen	PFS/TTP
Hanna 	Docetaxel Pemetrexed	2.9 2.9 (PFS)
BR.21 	Erlotinib Placebo	2.2 1.8 (PFS)
Shepherd 	Docetaxel Placebo	10.6w 6.7w (TTP)
TAX 320 	Docetaxel Vin or ifos	8.5w 7.9w (TTP)

While a PFS that matched the best previously demonstrated second line results would be sufficient to meet the threshold for further study, several factors are worthy of note in considering how such results could be interpreted and utilized. First, both SRS and erlotinib are substantially less toxic than cytotoxic chemotherapy. Second, this therapy would represent an additional option for EGFR mutant patients—after second progression on erlotinib, patients would still be eligible for treatment with standard chemotherapy. Thus, we hypothesize that the proposed treatment strategy will lead to a median progression free survival of at least 3 months.

A median PFS of 3 months implies that at 3 months, 50% of the population will still be progression free (PF). With 40 patients, the following table shows the precision of the 95% confidence interval that will be constructed for the percentage of patients who are PF at 3 months. If the percentage of patients PF at 3 months is 65% the 95% CI will be (48%-79%).

Number of Pts Progression Free at 3 months	3 month PFS (95% CI)
16/40	40% (25%, 57%)
18/40	45% (29%, 62%)
20/40	50% (34%, 66%)
22/40	55% (38%, 71%)
24/40	60% (43%, 75%)
26/40	65% (48%, 79%)
28/40	70% (53%, 83%)

We expect the percentage of patients who are PF at 3 months to be more than 50%, so with 40 patients, if 65% or 70% of patients are PF at 3 months, the exact 95% binomial confidence interval will be sufficiently narrow and suggest that the median PFS is longer than 3 months. An exact binomial test with a nominal 0.05 one-sided significance level will have 80% power to detect the difference between the null hypothesis of 50% PF at 3 months and the alternative hypothesis of 70% PF at 3 months when the sample size is 40.

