### **8.3 Data Analyses Plans**

Kaplan-Meier curves with appropriate confidence bands will be used to estimate the primary endpoint of median progression free survival. An exact 95% binomial confidence interval for the percentage of patients progression free at 3 months will be also be constructed, and a one-sided test will be done to see if it significantly higher than 50%. While the primary objective is to estimate median PFS, with 40 patients, we may be able to detect a significant improvement over a null hypothesis of only 50% of patients being progression free at 3 months.

Appropriate descriptive statistics including means, standard deviations, medians, and ranges will be provided for continuous data (ex. proteomics), and proportions will be used to summarize categorical data (ex. control and toxicity rates). Standard Kaplan-Meier curves and Cox proportional hazard models will be used to analyze time to event endpoints (including secondary endpoint of OS).

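### No rule back-dates progression when an enlarged SRS-treated lesion is first watched and later judged progressive, so as written the event takes the later date, usually past the 3-month landmark.

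*Combined protocol and SAP*

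**What the plan says.** The PFS clock is set in Section 6.9.1: "Progression free survival will be measured from the time of initiation of SRS until the time of progression or death". The same section explains that irradiated areas can inflame without true progression. It therefore provides that "clinician judgment will be used for both protocol and treatment decisions in evaluating whether a lesion treated with SRS that appears larger" is really progressing, and it requires one and the same judgment for study evaluation and clinical care. It gives no size threshold, time limit or confirmation step for that judgment.

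Section 6.9.2, written for local control of the same lesions, adds that "observation over time may be necessary for definitive assessment of some lesions". Section 6.4 says that at progression on erlotinib "the time of documented progression will be recorded".

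On the analysis side, Section 8.2 states that "An exact binomial test with a nominal 0.05 one-sided significance level will have 80% power" to separate "the null hypothesis of 50% PF at 3 months" from "the alternative hypothesis of 70% PF at 3 months when the sample size is 40". Section 8.3 makes a Kaplan-Meier estimate of median PFS primary. It adds "An exact 95% binomial confidence interval for the percentage of patients progression free at 3 months" and a one-sided test of that percentage against 50%.

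No section says which date applies when a lesion first read as inflammation is later judged progressive. No sensitivity analysis is planned on the point. The progression definition in Section 6.9.10 makes no exception for SRS-treated lesions and is not reconciled with Section 6.9.1.

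**The concern.** The clinical reason for using judgment is stated in the plan and is not in dispute. The issue is the date given to the event once the judgment is made.

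Take a patient whose only abnormal finding at the first scan is a larger treated lesion. The clinicians reasonably choose to watch it, and at the second scan they call it progressive. Progression is documented at the second scan, and Section 6.4 records that time. The first scan normally falls before 3 months and the second after. Watching the lesion therefore turns a failure on the tested endpoint into a success and moves the event about 8 weeks later on the Kaplan-Meier curve. The trial is single-arm and open-label, and the hypothesised median is only 3 months. If the date is left to be settled after the data are seen, the reader cannot tell how far the result depends on it.

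**Working it through.** **1. Reproduce the planned test.** Inputs from Section 8.2: N = 40, null 50%, alternative 70%, one-sided nominal 0.05. The exact rejection rule is the smallest r with P(X ≥ r | 40, 0.50) ≤ 0.05.

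- r = 25: P = 0.077, too large.
- r = 26: P = 0.040, so the rule is 26 of 40.
- Power: P(X ≥ 26 | 40, 0.70) = 0.807, which agrees with the stated 80%.
- The exact interval for 26/40 is 48.3% to 79.4%, which agrees with the Section 8.2 table.

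**2. Place the scans against the landmark.** Three months is 3 × 365.25 / 12 / 7 = 13.04 weeks from SRS start. The key to the Section 6.1 table sets visits every 8 weeks ± 1 week after erlotinib initiation, with tumor measurements up to 7 days before the visit. Section 4.3 recommends restarting erlotinib 3 days after SRS and allows it sooner. Section 4.2.2f allows up to 10 daily fractions, which run from day 0 to day 11.

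| Case | Scan 1 (weeks) | Scan 2 (weeks) |
|---|---|---|
| One-day SRS, erlotinib at once | 7 − 1 = 6, to 9 | 15 − 1 = 14, to 17 |
| 10 daily fractions plus 3 days (11 + 3 = 14 days = 2 weeks) | 8 to 11 | 16 to 19 |
| Earliest extreme: both visits a week early, scan a week before the visit | 6 | 7 + 7 − 1 = 13.0 |

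Scan 1 precedes 13.04 weeks in each case. Scan 2 follows it except in the extreme case, where it falls on the landmark itself.

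**3. Effect on the test.** The documents do not give the number of patients affected, so a range is assumed. Let the true rate, dated at first enlargement, be 50%, and let an expected k of 40 patients be shifted past 3 months. The reported rate is then 0.50 + k/40, and the rejection probability is P(X ≥ 26 | 40, 0.50 + k/40).

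| k (share of the 20 expected failures) | Reported rate | P(significant) |
|---|---|---|
| 0 | 50% | 0.040 |
| 1 (5%) | 52.5% | 0.076 |
| 2 (10%) | 55% | 0.133 |
| 3 (15%) | 57.5% | 0.213 |

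**4. One patient at the boundary.** A true 25/40 is 62.5% (95% CI 45.8% to 77.3%, one-sided p = 0.077). With one patient shifted it is reported as 26/40 (65%, p = 0.040).

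**5. Effect on the Kaplan-Meier estimate.** Each shifted event moves from scan 1 to scan 2, about 8 weeks. With 40 patients and no earlier censoring, each such patient raises the curve by 1/40 = 2.5 percentage points between the two scans. Whether the median moves depends on where the curve crosses 50%.

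**The case against.** The strongest reply is that the plan nowhere states that the event is dated at the final call. Section 6.4 is a visit procedure, the observation sentence belongs to local control, and Section 6.9.1 itself contains no deferral wording. This stands in part. A reader might infer that the protocol prescribes counting true failures as progression free. It does not: back-dating is neither required nor forbidden, and the later date follows from reading three sections together. But Section 6.9.2 refers back to the same lesions, and the time of documented progression is the only dating instruction given.

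The requirement to use the same judgment for study and clinic is a real safeguard on the decision. It does not govern the date, because a sound decision to keep watching still produces the later one.

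Frequency is unknown. A patient is affected only if an enlarged treated lesion is the sole sign at scan 1, is not called progressive then, and is called progressive later. New lesions or progression elsewhere still count at scan 1. The 94% crude local control in Section 1.4.2 comes from another cohort over its whole follow-up and gives no 8-week rate.

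The 3-month test is also secondary to estimating median PFS, so type I error is not the whole consequence.

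Two further inferences are tempting and unsupported. A reader might conclude that every error favours the treatment. Late dating does only lengthen PFS, but judgment can also call inflammation progression, which shortens it. A reader might also conclude that local control is inflated. Section 8.3 reports control as a proportion and no section sets a time point for it, so a lesion finally judged progressive is a local failure whatever its date.

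**Conclusion.** The gap is real and should be closed. Following the text as written, an enlarged treated lesion that is watched and then judged progressive is dated at the later scan. Under the usual schedule this moves the event past the 3-month landmark and about 8 weeks later in the PFS estimate.

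If 1 to 3 of 40 patients are affected and the true rate is 50%, the chance of a significant test is about 0.076 to 0.213 instead of 0.040. A single patient can decide a borderline result. These figures rest on an assumed number of shifted patients, on enlargement at scan 1 being true progression in those patients, and on the scan windows not compounding to their earliest extreme. The documents support the mechanism and its direction. They do not support any claim about how often it will happen.

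**What to change.** Add to Section 6.9.1: if a treated lesion first judged inflammatory is later judged progressive at the same site, progression is dated at the first scan that showed the enlargement. Record that date on the eCRF alongside the date of the final call.

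Add to Section 8.3 a pre-specified sensitivity analysis of the 3-month rate and median PFS:

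- results under both dates, first enlargement and final call;
- a lower bound that counts as progression any treated-lesion enlargement meeting Section 6.9.10 (sum of target diameters) or Section 6.9.11 (unequivocal non-target progression).

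The lower bound has to use these rules as they stand. A strict lesion-by-lesion size classification would not fit, because progression of target lesions is judged on the sum of diameters. Section 6.9.9 also caps targets at five in total and two per organ and requires no measurements for other lesions, so some treated lesions may have no recorded diameter.

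The cost is a few sentences, one eCRF date and the extra analyses. No scan, visit, reader or treatment decision changes. Reported PFS may be slightly less favourable. Back-dating can also place an event too early when true inflammation is followed by later regrowth, which is why both dates should be reported. The lower bound will count some genuine inflammation as progression and should be labelled accordingly.
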